| 18.4 | Publication Plan | 36 |
| 19.0 | REFERENCE LIST | 37 |

SUMMARY

| | |
|---------------------------|---|
| Title | Long Term Follow-up Study of CTN 236 - A Study of an HPV VLP Vaccine in a Cohort of HIV Positive Girls and Women |
| Goal | We hypothesize that HPV antibody levels in HIV-positive girls and women will decline more rapidly and more significantly than in HIV-negative girls and women and that this decline will be determined by HIV parameters. |
| Study population | HIV-positive girls and women (greater than, or equal to, age 11) attending the HIV treatment clinic that are currently enrolled in CTN 236 study will be invited to participate in the 5 year long term follow-up study. |
| Objectives | |
| Primary | To measure the antibody response to each genotype contained in the qHPV vaccine out to 96 months post-vaccination regimen. |
| Secondary | 
1) To determine the incidence rate and nature of 'breakthrough' HPV incident and persistent (2 sequential positive HPV DNA in > 6 months) infections of vaccine- non-vaccine-containing high-risk types;2) To determine the incidence rate of cervical dysplasia (LSIL or greater) and/or vulvar and vaginal dysplasia associated HPV genotypes (both with and without vaccine- types); and3) To determine the incidence rate of external genital warts. |
| Exploratory | 
1) To examine the relationship between HSV-2 serostatus and peak HPV antibody response as well as HPV incident and persistent infections; and2) To relate vaginal microbiome profiles to HPV acquisition/persistence and cervical dysplasia. |
| Timeline | First Visit, First Subject (FVFS): 10 June 2015 Last Visit, Last Subject (LVLS): 30 March 2019 |
| Study design | A longitudinal cohort follow up study of girls and women aged 11 years of age and older who participated in the study, "A Study of an HPV VLP Vaccine in a Cohort of HIV Positive Girls and Women (CTN 236)" |
| Inclusion Criteria | 
• Enrolled in CTN 236 study• Able to give fully informed consent or assent |

Research Protocol
Long Term Follow-up Study of CTN 236 - A Study of an HPV VLP Vaccine in a
Cohort of HIV Positive Girls and Women

| | |
|---|--|
| Exclusion Criteria | 
 • Did not receive at least one vaccination via CTN 236, phase 1 • Cannot provide fully informed consent or assent |
| Duration of study for each subject | 
Up to 60 months
 
Subjects will participate in up to 3 possible study visits over a total of 5 years. Duration of time since vaccination as part of CTN 236 varies depending on when they were enrolled; therefore, to ensure all subjects are offered participation in the long term follow up, 6 possible visit times have been created.
 |
| Visit schedule | Main Study Procedures (no standard clinical or sub-study procedures) |

| | Informed Consent/ Assent | Health Questionnaire | Study Blood Work | Cytology and HPV DNA & vaginal swabs* | SAE and Con Med Assessment |
|------------------------|-----------------------------|----------------------|------------------|---------------------------------------|----------------------------|
| Month 36 (Visit 8) | X | X | X | X | X |
| Month 48 (Visit 9) | X | X | X | X | X |
| Month 60 (Visit 10) | X | X | X | X | X |
| Month 72 (Visit 11) | X | X | X | X | X |
| Month 84 (Visit 12) | X | X | X | X | X |
| Month 96 (Visit 13) | X | X | X | X | X |

* Those girls and women who are pre-menarchal or never sexually active will not have any pelvic examinations, clinical Pap smears, or study genital sampling until post-menarchal and sexually active.

Complete outline of all procedures found in table 7.3

| | |
|--|---|
| Data collection | Template recruitment documents, consent and source documents will be provided by the Study Coordinating Centre. Source data will be transferred to paper case report forms and sent to the CIHR Canadian HIV Trials Network (CTN) where it will be entered into an electronic database. |
| Monitoring | This study is being conducted according to the following: International Committee on Harmonization (ICH) Guidance Document E6: Good Clinical Practice (GCP): Consolidated Guidelines. Site monitoring will be performed to ensure compliance with the above. |
| Data Safety Monitoring Board (DSMB) | The established CTN data safety monitoring committee with additional expertise in pediatrics and gyne-oncology will provide oversight and monitoring of the conduct of the study to ensure the safety of the subjects. Additionally, the DSMB will ensure the validity and integrity of the study data. |

LIST OF ABBREVIATIONS

| | |
|--------------|---|
| AE | Adverse event |
| AIDS | Acquired immunodeficiency syndrome |
| ART | Antiretroviral therapy |
| ARV | Antiretroviral |
| BCCDC | British Columbia Centre for Disease Control |
| CPARG | Canadian Pediatrics AIDS Research Group |
| CIN | Cervical intraepithelial neoplasia |
| CIS | Carcinoma in situ |
| CRF | Case report form |
| DAIDS | Division of AIDS Table for Grading the Severity of Adult and Pediatric Adverse Events |
| DNA | Deoxyribonucleic acid |
| DSMB | Data Safety Monitoring Board |
| CTN | CIHR Canadian HIV Trials Network |
| GCP | Good clinical practices |
| HAART | Highly active antiretroviral therapy |
| hCG | Human Chorionic Gonadotropin |
| HIV | Human Immunodeficiency Virus |
| HPV | Human Papillomavirus |
| ICH | International Conference on Harmonization |
| IM | Intramuscular |
| NIH | National Institutes of Health |
| Pap | Papanicolaou cervical smear |
| PCR | Polymerase chain reaction |
| PID# | Primary identification number |
| PRN | When necessary |
| Q-HPV | Quadrivalent Human Papillomavirus Vaccine |
| REB | Research ethics board |
| RNA | Ribonucleic acid |
| SAE | Serious adverse event |
| SOP | Standard operating procedure |
| STI | Sexually transmitted infection |
| STM | Specimen transport media |
| VLP | Virus-like particles |
| WHRI | Women's Health Research Institute |

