3.0 OBJECTIVES

The overall goal of the study is to determine the immunogenicity and efficacy of the HPV vaccine out to 4 years in an established cohort of HIV-positive girls and women in Canada.

1. Primary

To measure the antibody response to each genotype contained in the qHPV vaccine out to 96 months post vaccination regimen.

2. Secondary

- 1) To determine the incidence rate and nature of 'breakthrough' HPV incident and persistent (2 sequential positive HPV DNA in > 6 months) infections of vaccine- non-vaccine-containing high-risk types;
- 2) To determine the incidence rate of cervical dysplasia (LSIL or greater) and/or vulvar and vaginal dysplasia associated HPV genotypes (both with and without vaccine- types); and
- 3) To determine the incidence rate of external genital warts.

3. Exploratory

- 1) To examine the relationship between HSV-2 serostatus and peak HPV antibody response as well as HPV incident and persistent infections;
- 2) To relate vaginal microbiome profiles to HPV acquisition/persistence and cervical dysplasia.

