| Month 72 (Visit 11) | First Dose + 72 months (+/- 2 months) | X | X | X | X | X | X | X |
| Month 84 (Visit 12) | First Dose + 84 months (+/- 2 months) | X | X | X | X | X | X | X |

Research Protocol
Long Term Follow-up Study of CTN 236 - A Study of an HPV VLP Vaccine in a
Cohort of HIV Positive Girls and Women

| | | | | | | | | |
|------------------------|---|---|---|---|---|---|---|---|
| Month 96 (Visit 13) | First Dose + 96 months (+/- 2 months) | X | X | X | X | X | X | X |
|------------------------|---|---|---|---|---|---|---|---|

* Those girls and women who are pre-menarchal and not sexually active will not have any pelvic examinations or Pap smears until post-menarchal and sexually active or at discretion of the site investigator.

Due to variation in duration of time since first dose of vaccine, some subjects are out of window for Month 36 and Month 48, e.g. it has been more than 48 months since first dose of vaccine was received. Therefore, we have extended the study visit timeline up to and including Month 96 post-vaccine, also designated Visit 13. Visits will occur annually until project grant is completed (March 31, 2019).

4. Study Visits

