11.0 SUBJECT COMPLETION AND WITHDRAWAL

Investigators or their delegates will attempt to contact those study subjects who do not return for study visits. Study personnel will make at least three attempts to contact the subject using various communication means. Each attempt should be documented in the subject source documents.

A subject completing three annual visits up to and including Month 96/Visit 13 will be considered to have completed the study.

Withdrawals will not be replaced. All withdrawals will be documented including the date of the withdrawal and the reason.

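### The stated 60 months (5 years) per participant cannot fit a 45.6-month study; the visit rules need reconciling, and Section 16.2(c) omits first-dose date although no HIV-positive participant can supply both Month 36 and Month 96

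*Combined protocol and SAP*

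**What the plan says.** **Duration.** The Summary's timeline reads "First Visit, First Subject (FVFS): 10 June 2015 Last Visit, Last Subject (LVLS): 30 March 2019". Its study-population row says that participants "will be invited to participate in the 5 year long term follow-up study". Its row on duration per subject gives a maximum of 60 months and adds: "Subjects will participate in up to 3 possible study visits over a total of 5 years".

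**Number of visits.** Section 11.0 states: "A subject completing three annual visits up to and including Month 96/Visit 13 will be considered to have completed the study". The note under the visit table in Section 7.3 explains that for some subjects "it has been more than 48 months since first dose of vaccine was received", extends the schedule to Month 96, and continues: "Visits will occur annually until project grant is completed (March 31, 2019". That note states no cap.

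**Horizon and time origin.** Section 3.0 sets the overall goal as to "determine the immunogenicity and efficacy of the HPV vaccine out to 4 years". The primary objective runs "out to 96 months post vaccination regimen". The visit windows in Sections 7.3 and 7.4.2 count from the first dose, with a tolerance of 2 months either side.

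**Analysis.** Section 16.2(c) models antibody response at Months 36, 48, 60, 72, 84 and 96 from first dose using GEE. The HIV comparison is adjusted for age and includes an HIV by time interaction. A further model is fitted to the HIV-positive participants alone. Neither names a term for first-dose date or entry cohort.

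**The concern.** The per-subject duration conflicts with the calendar dates in the same Summary. A reader would credit each participant with 5 years of follow-up when the most anyone can have is about 3.8.

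The visit rule matters because Month 96 is the far end of the primary objective. A limit of three visits and an uncapped annual schedule can lead sites to stop collecting samples from the same person at different points.

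The analysis treats Months 36 to 96 as one time axis. Participants join it at different points according to when they were first vaccinated, and none in the HIV-positive cohort can cover the whole of it. Overlapping within-person series link the visits, but the contrast between the two ends is between different people. If antibody level differs by enrolment period, some of that difference can be read as waning.

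**Working it through.** **Inputs.** First and last visit dates (Summary, Timeline); visit months and the tolerance of 2 months (Sections 7.3 and 7.4.2); three-visit limit (Summary and Section 11.0); annual visits to 31 March 2019 (Section 7.3 note). One month is taken as 30.4375 days when days are converted.

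**1. Duration**
- 10 June 2015 to 30 March 2019 = 1389 days. 1389 / 30.4375 = 45.6 months; 1389 / 365.25 = 3.80 years.
- The plan's figure of 60 is reproduced only as 96 − 36, the width of the visit grid.
- Overstatement: 60 − 45.6 = 14.4 months.
- A run of k annual visits spans 12(k − 1) months, give or take 4 with the windows: three span 24 (20 to 28), four span 36 (32 to 40), five span 48 (44 to 52). Three or four fit on nominal dates. Five fit only at the window extremes.

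**2. Visit rule and Month 96**
- A fourth visit at 12-month spacing needs a first visit by 30 March 2019 − 36 months = 30 March 2016.
- Three consecutive annual visits ending at Month 96 are Months 72, 84 and 96. Someone who starts at Month 60 reaches Month 96 only as a fourth visit.
- The Month 96 window opens at Month 94: 30 March 2019 − 94 months = 30 May 2011, the latest usable first dose.
- If entry is at the first open window, starting at Month 72 requires the Month 60 window (closing at Month 62) to have shut by 10 June 2015. 10 June 2015 − 62 months gives a first dose before 10 April 2010.
- From 10 April 2010 to 30 May 2011 is 415 days; 415 / 30.4375 = 13.6 months of enrolment for which the rule decides. Those first dosed before 10 April 2010 can give a Month 96 sample as a third visit under either rule.

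**3. Months 36 and 96 in the HIV-positive cohort**
- Shortest gap: 94 − 38 = 56 months, against 45.6 available. No participant can supply both, under either rule.
- The Month 36 window closes at Month 38: 10 June 2015 − 38 months = 10 April 2012, the earliest first dose for a Month 36 visit.
- From 30 May 2011 to 10 April 2012 is 316 days, so the two first-dose ranges do not overlap.
- Section 4.0 puts the parent protocol's follow-up at 24 months, so it supplies no Month 36 sample.

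**4. Illustration of how a trend could enter the slope.** Assume a linear time term, three-visit series, equal-sized entry groups and a linear trend in antibody level with first-dose date. The share of the trend entering the pooled slope is cB / (cB + W). B is the variance of the series starts. W = 96 is the variance of visit times 0, 12 and 24 within a series. c = (1 − ρ) / (1 + 2ρ) for within-person working correlation ρ, so c = 1, 0.125 and 0.036 for ρ = 0, 0.7 and 0.9.

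| Adjacent start slots | B | ρ = 0 | ρ = 0.7 | ρ = 0.9 |
|---|---|---|---|---|
| 2 | 36 | 27% | 4% | 1% |
| 3 | 96 | 50% | 11% | 3% |
| 4 | 180 | 65% | 19% | 6% |

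Example: 2 slots, ρ = 0: 36 / (36 + 96) = 0.27. With first-dose date in the model, the share of a linear trend that enters is zero.

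**The case against.** The strongest reply is that only the duration is a proven error. It feeds no sample size or other calculation, and correcting it is a wording change. That is right about its reach, but the figure is still wrong as written.

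A reader might infer that the two visit rules contradict each other and necessarily yield different Month 96 populations. The documents do not support that. The Summary and Section 11.0 agree on three visits, and the Section 7.3 note can be read as giving only frequency and an end date for the study. Even if it permits a fourth visit, the difference depends on prompt entry and no missed visits. Someone first dosed on 30 May 2011 who enters late can attend on 30 March 2017, 2018 and 2019, for Months 72, 84 and 96, and so reach Month 96 within three visits. No closing date for enrolment is given. What stands is an ambiguity to be resolved.

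Nor does the rule decide for everyone already past the Month 48 window at study start, since those first dosed before about 10 April 2010 reach Month 96 either way.

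A reader might also extend the lack of overlap to the comparator. Section 16.2(c) says individual HIV-negative data will be available at all six times, and those participants may span them.

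On the model, no enrolment trend is documented, and Section 4.0 puts most participants at 24 to 36 months from their vaccine course, so equal entry groups are unlikely. Since GEE is chosen to handle within-person correlation, working independence is not the obvious reading either. The larger percentages are therefore illustrations. It is tempting to ask for an exchangeable working correlation, but Section 16.3 uses time-updated HSV-2 status with GMT among the outcomes. With time-varying covariates, a non-independence structure can itself introduce bias. Naming one would also leave the lack of overlap as it is.

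Finally, the 4-year goal in Section 3.0 may simply be the 3.8-year study length rounded.

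**Conclusion.** The concern stands in three parts of unequal strength.

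- **Duration: certain.** On the stated dates nobody can take part for 60 months; the most possible is 45.6.
- **Visit rule: conditional.** The passages need reconciling. The 13.6 months of first-dose dates at issue assume that Section 7.3 permits a fourth visit, that entry is at the first open window and that no visit is missed.
- **Longitudinal model: the lack of overlap is certain for the HIV-positive cohort, its effect is not.** The Month 36 to Month 96 contrast is entirely between people with different first-dose dates, and the model has no term for this. Bias in the pooled slope requires an enrolment trend. The HIV by time interaction, which tests the hypothesis in Section 2.0, is affected only if the trend or the visit pattern differs by HIV group. Section 16.2(b), which models decline from peak separately, is less exposed.

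How many participants can reach Month 84 or 96 cannot be derived, because the documents give no first-dose dates. It would go too far to conclude that the waning estimate or the HIV comparison is biased. The change is worth making because it is cheap and concerns a primary analysis.

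**What to change.** 1. Restate the per-subject duration as at most about 46 months, or 24 nominal if three annual visits is the rule.
2. Reconcile the Summary, Section 3.0, the Section 7.3 note and Section 11.0 so that they give one number of visits, one horizon and one time origin (first dose or completed regimen).
3. In Section 16.2(c), add first-dose date as a covariate in the HIV-positive longitudinal model. Add it to the HIV-negative comparison as a sensitivity analysis if comparator dates are available.
4. State that Month 96 results in the HIV-positive cohort describe only those first dosed by about May 2011.

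The cost is wording and one model term. First-dose date is already needed to set each participant's visit windows; whether the comparator data hold it is not stated. The stated follow-up becomes less favourable, and the slope may lose a little precision.

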1.0 Background

1. Epidemiology and Burden of Disease

Worldwide, cervical cancer is the fourth leading cause of cancer-related death in women with 528,000 new cases and 266,000 deaths yearly.¹

Cervical cancer is the single greatest cause of death from cancer in women in sub-Saharan Africa, where HIV prevalence is exceptionally high particularly among young women.^{1,2,3} In countries with wide access to quality Pap smear screening, the burden of disease has shifted to pre-invasive dysplastic lesions. In Canada, for example, there is at least 50 times more pre-invasive disease in women than there is cervical cancer, which still represents a substantial economic, social and psychological burden to women.^{4,5} In spite of the pap screening program, there are over 350 deaths per year in Canada due to invasive cervical cancer (approximately 1 death every day)⁶, often as a result of late diagnosis due to inadequate Pap smear screening, especially in vulnerable populations including immigrant and Aboriginal women.⁷ This underlines a clear need to develop and evaluate preventative options.

The link between HPV and cervical cancer is well-established. HPV DNA is detected in 96.6% of cervical cancer tissue and the vast majority of cervical cancers can be attributed to HPV infection.⁸ Based on both epidemiologic and phylogenetic data, the high-risk HPV types, for cervical cancer, in frequency order, are: 16, 18, 33, 45, 31, 58, 52 and 35, and ***probably high risk*** are: 51, 56, 39 and 59.⁹ Overall, 70% of cervical cancer cases are caused by the two most common HPV types; 16 and 18 (high risk), and 90% of genital warts are caused by HPV 6 and 11 (low risk).¹⁰

The burden of disease in HPV infection outside the cervix is also important. HPV has been implicated in most non-cervical genital tract cancers, including penile and anal cancer, and in head and neck cancers. Cervical cancer incidence in a Canadian population is seen at 199.54 per 100,000 person/years (PY) in HIV positive women, compared to 47.5 per 100,000 PY in HIV negative women.¹¹ Fortunately, anal cancer has not been frequent in women, even women with HIV infection, with rates of 15.96 per 100,000 PY.¹¹ Research on the efficacy of this vaccine in preventing these cancers is also required.¹² As we did not conduct evaluations of baseline anal and oral HPV we are not in a position to conduct research into the efficacy of the HPV vaccine in this cohort to these types.

The affliction of disease from genital warts is also substantial. Data from the US suggests that genital warts are the most common sexually transmitted infection.¹³ HPV 6 and 11 cause up to 90% of genital warts. In women, genital warts may develop anywhere in the lower genital tract including the cervix, with multiple sites being common. Clinically visible warts are present in approximately 1% of sexually active adults.¹⁴ In persons with normal immune function, visible warts and evidence of viral replication are typically gone by approximately 18 months after initial

infection.¹⁵ However, in HIV-positive individuals the lesions can be significantly larger and very problematic to treat, highlighting the benefits of HPV primary prevention in this population.^{16,17} Of note, vaccination programs in HIV negative healthy populations are already showing decrease in genital warts,¹⁸ but no data is available on this response in HIV positive vaccinated persons.

2. Clearance and persistence of HPV

The role of the host immune system in regression of HPV infection is not fully understood but in regressing genital warts an infiltration can be detected of CD4 cells, CD8 cells and macrophages that likely represents a T-cell response to specific early proteins of HPV (E2 and E6).¹⁹ In HIV-negative women, most of these infections (80%) appear to 'clear'; that is, HPV DNA can no longer be detected on the mucosal or epithelial surface. The time required for this 'clearance' appears to vary with different HPV genotypes; ranging from 5-6 months for low risk types to 8-14 months for high-risk types.^{20,21,22} It is unclear whether the virus is completely eliminated, or if it remains latent in basal cells and could reactivate under immune permissive conditions. Risk of carcinogenesis appears to be directly related to the persistence of oncogenic (high risk) virus. The definition of transient or persistent infection has been defined in most studies as the presence of HPV DNA by polymerase chain reaction (PCR) at two consecutive assessments 6 months apart.²³

3. Natural HPV Immunology

Many nuances of HPV immunology are poorly understood, in particular the ability of the virus to evade the immune system. Natural immunity is generally not effective in protecting against re-infection with the same genotype.²⁴ Our current understanding is that the host's immune response to natural infection initially involves a local innate response, which then triggers circulating humoral (antibody) and cell mediated responses (e.g. CD4 and CD8 cells). The cell-mediated immune response is required for HPV containment and lesion regression.^{13,25} Persons with cell-mediated immune dysfunction, such as HIV-positive individuals, have higher rates of HPV infection. **HIV-positive women have much higher rates of cervical dysplasia and cancer than HIV-negative women and progress more rapidly from low grade to high grade lesions and to invasive cancer.**^{26,27} Of note, our recent study of cervical cancer in HIV-positive women in British Columbia has determined that HIV-positive women have 4.2 fold (2.72-6.20) higher rate of HPV associated female genital cancer than the general population.¹¹ The baseline rate of low-grade cervical dysplasia is approximately 13% in HIV-positive women compared to 4% in HIV-negative women.^{27,28} The problem is exacerbated in HIV endemic areas such as sub-Saharan Africa where Pap smear screening programs are largely lacking.²⁹

4. **HPV/ HIV interactions**

The T cell immune dysfunction caused by HIV infection offers a unique opportunity to study and better understand the interrelationship between the neutralizing antibody protection of the humoral immune system triggered by the vaccine, and HPV elimination that requires adequate T cell function. **The most valuable knowledge gained in this area will be a definition of an immune correlate of protection, i.e. a level of circulating antibody above which the majority of persons will be protected from acquisition of the infection. This new knowledge will be highly relevant to vaccine programming in Canada and globally.**

The interactions between HIV and HPV are not fully understood. HIV-mediated immune suppression appears to facilitate HPV persistence and its oncogenic potential. In part this appears to be due to direct enhancement of HPV integration in the presence of HIV.³⁰ The effect of HPV on HIV replication and viral load in the circulation and in the genital tract is not well characterized. Of note, HPV studies have typically involved interval evaluations of HPV shedding which has led to a poor understanding of the longitudinal process of infection, persistence, clearance, and reinfection or reactivation.²³ In some studies to date, combination antiretroviral therapy (cART), presumably through immune function reconstitution, results in higher rates of clearance compared to those not on cART.^{31,32,33} However, in other studies, cART and CD4 counts have not been well correlated with clearance and in fact HIV suppression and inversely HIV replication (higher viral load) has been associated independently.³⁴ Some of the difficulty has been the prior study designs. Data from our study group prior to the availability of HPV vaccine showed that there was a differential response to immune suppression and infection with HPV 16 in that perhaps HPV 16 is such a potent oncogenic genotype that it can cause disease regardless of immune function.^{24,31}

5. **HPV prevalence is high in HIV-positive cohort studies**

Our studies and others have shown that HPV is highly prevalent in HIV positive populations. Even in a post HAART era, clearance is still diminished compared with HIV negative populations and this underscores the need to better understand the role of HIV replication and HPV infection and the HPV immune response. Data from the Canadian Women's HIV study group found high risk HPV genotypes, as detected by genital tract sampling in HIV-infected women, in the following order of frequency: 52, 84, 16 and 83.³⁵ In this cohort (n=198, samples=437), 62.1% of women were HPV positive at least once for one or more of the 27 HPV types tested, with 7.6% positive for 6/11, 15.7% positive for 16/18, and 1.0% positive for 6/11 & 16/18. In an international study, 77% of HIV-positive women had HPV detected at least once (incident infection). HPV 16 was the most frequent genotype, with mixed infection seen in 26%.³⁶ Persistent infection was seen in 41.5% of women but there was no relationship between HPV infection status and CD4 cell count or HIV viral

load. This compares to a 2.6% HPV 16 persistence seen in the HIV-negative women in the placebo arm of the large HPV 16/18 trial.³⁷ Furthermore, an improved response to treatment for cervical dysplasia was observed for women on highly active antiretroviral therapy (HAART).³⁸ Similar data were seen in other cohorts including a South African study demonstrating rapid increase in HPV infection after HIV seroconversion³⁹ and in a US cohort with relatively high HPV prevalence and higher rates of cervical dysplasia in women with lower CD4 cell counts.⁴⁰ Some studies have shown a similar 16, 18 genotype dominance in HIV-positive women compared to HIV-negative women in causing cervical dysplasia and cancer.^{41,42,43,44} However in other studies multiple type infections and non 16/18 oncogenic HPV were associated with persistence, cervical dysplasia and cancer, highlighting the importance of cross-protection, and/or multivalent vaccines in HIV positive populations.^{45,46,47}

6. HPV, other STI's and the vaginal microbiome

Elucidating the role of HSV-2 in contributing to HPV persistent infection and oncogenic progression is important because HSV-2 co-infection is common, with an estimated seroprevalence of 55% in Canadian HIV-infected populations.⁴⁸ Safe and inexpensive antiviral drugs can be used both for direct treatment but also for treatment as prevention by suppressing HSV viral shedding in an infected person and substantially decreasing risk of transmission to an uninfected person.^{49,50} Existing data on the role of HSV-2 in cervical dysplasia are unclear. While several studies have observed an association between HSV-2 co-infection (defined either serologically or by the presence of HSV-2 DNA in cervical samples) and cervical cancer, this relationship has sometimes^{51,52,53,54} but not always^{55,56} persisted after adjustment for HPV DNA. However, most studies were limited by their use of HSV-2 serology assays with poor specificity (e.g. based on whole virus or crude lysate⁵⁷), and to our knowledge there are no prior studies in the setting of HIV infection. The rich clinical and microbiologic data within our HPV vaccine in HIV positive girls and women study provides a unique opportunity to evaluate the role of herpes simplex virus type 2 (HSV-2) as a cofactor in progression to cervical dysplasia among HIV-infected women.

There has been increasing evidence of the interrelationship between the composition of the endogenous lower genital tract microbiota and the risk of acquisition and/or transmission of genital pathogens, including HIV and HPV.^{58,59,60,61,62} These findings suggest there are relationships between microorganisms in a given niche, and provide evidence to support the hypothesis that a healthy vaginal microbiome may be protective against pathogens. Dysbiosis of the vaginal microbiome is associated with increased susceptibility to human papillomavirus (HPV) infection, and may also influence progression of HPV to cervical cancer.^{63,64} Although we understand that HPV infection is a prerequisite for the development of cancer of the uterine cervix, we are also beginning to understand the ability of other infections or perturbations of the vaginal ecology to affect acquisition of HPV, persistence of HPV, and the ability of this virus to cause cervical dysplasia and cancer. The complexity of this

interplay is intricate and only understood in a very limited fashion. A microbial ecology approach is required to fully understand these phenomena. Our investigator team, which includes members funded through the CIHR Canadian Microbiome Initiative to study the vaginal microbiome utilizing a metagenomic approach, is well equipped to explore these issues. This collective expertise will permit the profiling of the bacteriome associated with oncogenic HPV persistence and/or integration into the host genome, and will enable future personal profiling of cervical cancer risk based on microbiome profiles.

7. **HPV Vaccines**

The two currently licensed vaccines designed to prevent HPV infection, have been tested in large clinical trials. There is a bivalent vaccine against HPV 16 and 18 (GlaxoSmithKline, GSK) and a quadrivalent vaccine against HPV 6, 11, 16 and 18 (Merck). In addition, a 9-valent vaccine is currently being investigated in large scale clinical trials, with positive safety, immunogenicity and efficacy data under review by the FDA. These vaccines are produced as virus-like particles (VLP's) based on the L1 capsid protein gene of the virus inserted in insect or yeast vectors. These proteins self-assemble into protein shells with identical configuration to the native virus, but without DNA, and so are deemed subunit, protein vaccines. Safety, efficacy, and immunogenicity data on these vaccines in HIV-negative populations of young women are based on clinical trials conducted by GSK and Merck, respectively, with some follow up post-licensure trials now in progress. Both have shown remarkable safety profiles in otherwise healthy young HIV-negative women, with limited local injection site reactions as the primary side-effect and no evidence for differences in serious adverse events between vaccine and placebo arms.⁶⁵

Immunogenicity to the quadrivalent vaccine has been well studied in HIV-negative populations, showing that anti-HPV 6, 11, 16 and 18 geometric mean titers (GMT) were highest at month 7 (1 month following the final dose 3). Anti-HPV GMT's declined thereafter but reached a plateau at month 24 and remained stable through 5 years.^{66,67,68} In the original immunogenicity study by Villa et al.,⁶⁷ 100% of the subjects who were antibody negative to the relevant HPV type at baseline had a detectable antibody response at month 7 to HPV 6, 11, 16 and 18 respectively. These levels were 10-to 10⁴-fold higher than natural antibody levels in placebo recipients who were vaccine type positive at baseline.

8. **HPV vaccine implementation**

Currently, Canada has established a population level HPV vaccination strategy through school-based publicly-funded programming. As yet, the impact of this is limited by uptake and by the relatively young age of the public based program. Individuals who are not eligible in the public program and who have the means are able to pay for the vaccine, but vulnerable populations who cannot afford the vaccine lack access and continue to acquire HPV infection unnecessarily. It is vital to understand how best to protect our most vulnerable persons from HPV infection

and the risk of invasive cervical cancer. The implications of the vaccine programme for Pap smear screening is yet to be fully understood and therefore current screening schedules have not been adjusted. It is hoped that the vaccine will be particularly useful in preventing disease in women who have difficulty accessing Pap smear screening, e.g. Aboriginal women and Asian immigrant women who have shown low access to and uptake of Pap smear screening.^{69,70,71,72,73}

9. **Global HPV vaccine implementation plans**

Globally 266,000 women die every year, and without significant changes, this is estimated to be 416,000 by 2035. In resource-limited areas such as Africa, with little or no access to Pap smear screening, cervical cancer not only kills women, but its incidence is greatly exacerbated by the high prevalence of HIV infection. Cervical cancer incidence in South Africa is 174.8 per 100,000. In India, it is even higher at 186.5 per 100,000.⁷⁴ Safe and effective HPV vaccines would be of immense value in countries with such high rates of cervical cancer, especially in the absence of widely implemented screening programs. The World Health Organization (WHO) has demonstrated the capability of implementing large-scale vaccine programs. For example in 2003, global coverage of three doses of the diphtheria-tetanus-pertussis combination vaccine reached 78%.⁷⁵ Even complicated, comprehensive antiretroviral therapy rollout has been impressive with UNAIDS estimating that almost 10 million people in resource-constrained countries were on antiretroviral therapy at the end of 2012.⁷⁶ The Global Alliance for Vaccine and Immunisation (GAVI) is negotiating affordable three-tiered pricing for countrywide roll-out now with a number of low-income countries. The rational implementation of HPV vaccination programs in these areas is dependent on a sound understanding of the impact, safety, and efficacy of vaccination in HIV-positive persons who may be at varying stages of immune dysfunction.⁷⁷ As of February 4 2014, 10 additional countries were added as recipients of HPV vaccine rollout (to a total of 21 countries). This is to be primarily implemented using a 3 dose schedule but some pilot projects have opted for a 2 dose schedule, based on Canadian data from some of our investigator group. Although, we are confident in healthy Canadian HIV-negative girls, 2 doses of the vaccine provides equivalent antibody levels to 16-26 year old women who are well protected with these levels, this dosing regimen has not been tested in HIV positive populations. This greatly increases the urgency to determine the immunogenicity and efficacy for areas with high rates of HIV prevalence.

10. **HPV vaccine in HIV positive studies**

Our study group was one of the first groups globally to study one of these vaccines in HIV-positive, immune compromised populations. As the qHPV vaccine GARDASIL™ (Merck), which contains subtypes 6 and 11 (responsible for 90% of genital warts) and subtypes 16 and 18 (responsible for 70% of cervical cancer) was the first to be licensed and available in Canada for post-licensure studies, we engaged with Merck to permit an initial study of the safety and immunogenicity of this vaccine in a cohort of HIV-positive girls and women. Data from this cohort has

provided valuable information about the health of Canadian women and girls living with HIV. At the initial screening visit more than 80% of subjects were negative to HPV genotypes 6, 11, 16 and 18, found in the qHPV vaccine. This was a higher seronegative rate than seen in a US based study in which only 55.6% were HPV 16 negative and 73.7% HPV 18 negative at baseline, despite being a younger cohort overall (N=99, mean age 21.4 years).⁷⁸ Preliminary data outlined that in our study, 17 % of HIV-positive women had low-grade squamous intraepithelial lesions (LSIL) or greater at screening and 29% had at least one strain of oncogenic HPV present. It was observed that greater numbers of oncogenic HPV types were present in those women with cervical dysplasia.⁷⁹

